## 9. BLOOD EOSINOPHILS

- Blood eosinophil analyses will be based on the “Pharmacodynamic” population.
- Blood eosinophil values will be  $\log_e$ -transformed prior to summarising. Non-detectable values of 0 GI/L, will be replaced by half of the lowest observed detectable (non-zero) value in the study data set, prior to log transformation.
- Blood eosinophil values will be summarised by visit, and by visit and baseline mepolizumab use.
- Blood eosinophil values will also be summarised by visit, baseline mepolizumab use and injection site. These summaries will be performed only for the subset of subjects using the same injection site throughout the study.
- Absolute and ratio to baseline blood eosinophils will be listed.

Full details of data displays to be presented are given in [Appendix 8](#): List of Data Displays.

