# 9.2. Sample Size Considerations

# 9.2.1. Sample Size Assumptions

No formal sample size calculations were performed. Assuming a 30% screen failure rate, approximately 225 subjects will be screened in order to enrol 158 subjects (attempting at least one self-administration of mepolizumab). Assuming a dropout rate of up to 5% during the study, 158 enrolled subjects should provide at least 150 subjects with complete study data. Approximately 100 subjects will use autoinjectors with labelling that includes a pictogram plus standard labelling elements and 50 subjects will use the standard labelling without the pictogram.

No sample size re-assessment/adjustment is planned.

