## 9.3. Data Analysis Considerations

Full details of all pre-specified analyses will be described in the Reporting and Analysis Plan (RAP).

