## 9.4.3. Pharmacodynamic Analyses

Ratio to baseline (Visit 2) in blood eosinophil count will be summarized by visit, using summary statistics appropriate for log-normal data, overall, by previous mepolizumab use (i.e. not receiving mepolizumab treatment at Visit 1 or receiving 100 mg SC mepolizumab administered for the treatment of severe eosinophilic asthma every 4 weeks for at least 12 weeks prior to Visit 1) and by injection site. Values below the lower limit of quantification will be imputed as half the lower limit of quantification.

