## 2. SUMMARY OF KEY PROTOCOL INFORMATION

### 2.1. Changes to the Protocol Defined Statistical Analysis Plan

An additional analysis population was defined for reporting screen failures and inclusion/exclusion criteria deviations. This population is described in Section [4](#).

There are no other changes to the protocol defined statistical analysis plan.

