
 
• To assess mepolizumab plasma trough concentrations (<math>C_{trough}</math>) following the SC administration of mepolizumab liquid drug product in autoinjector.
 
	
 
• Mepolizumab plasma trough concentrations (<math>C_{trough}</math>) at Weeks 4, 8 and 12
 

 
• To assess the pharmacodynamic (PD) effect following the SC administration of mepolizumab liquid drug product in autoinjector.
 
	
 
• Ratio to baseline of blood eosinophils at Weeks 4, 8 and 12
 

 
• To assess the frequency of asthma exacerbations.
 
	
 
• Incidence of asthma exacerbations, expressed as the number of subjects with at least one exacerbation
 

Safety Objectives	Safety Endpoints

 
• To evaluate the safety and tolerability of mepolizumab liquid drug product in autoinjector.
 
	
 
• Incidence and frequency of Adverse Events (AEs) / Serious Adverse Events (SAEs) including systemic reactions and local injection site reactions
 
• Clinically significant change in haematological and/or clinical chemistry parameters
 
• Vital signs
 
• 12-lead electrocardiogram (ECG)
 
• Incidence of immunogenicity
 
• Level of self-reported pain immediately following, 1- and 24-hours following each injection (patient diary)
 

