
 
● Data recorded at the early withdrawal visit will be re-assigned in the ADaM data sets to the next scheduled visit, unless information already exists at that visit. Early withdrawal data re-assigned to a scheduled visit will be reported at that visit in summary tables and figures. Early withdrawal visit data that is not re-assigned to a scheduled visit will not be included in summary tables or figures by scheduled visit. However early withdrawal data that is not re-assigned to a scheduled visit will be considered in the derivation of highest/worst case post-baseline result for the summary tables.
 
● Data from all early withdrawal visits will be included in listings and individual subject figures.
 
	
Descriptive Summary Statistics	
Continuous Data	Refer to IDSL Statistical Principle 6.06.1
Categorical Data	N, n, frequency, %
Reporting of Pharmacokinetic Concentration Data	
Descriptive	Refer to IDSL Statistical Principle 6.06.1

Reporting Standards	
Summary Statistics	Assign zero to non-quantifiable (NQ) values (Refer to GUI_51487 for further details)
Graphical Displays	

• Refer to IDSL Statistical Principals 7.01 to 7.13.

	

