### 14.5.2. Handling of Missing Data

Element	Reporting Detail
General	
 
• In general, analysis will be performed on all available data and no imputation will be performed for missing data. However, if there are withdrawals from the study due to issues pertaining to the use of the autoinjector, a sensitivity analysis of the primary analysis will be performed. Missing or “not attempted” injection success assessments following these withdrawals will be imputed as injection failures i.e. unsuccessful attempts to self-administer mepolizumab in this sensitivity analysis.
 
• Missing data occurs when any requested data is not provided, leading to blank fields on the collection instrument. These data will be indicated by the use of a “blank” in subject listing displays, unless all data for a specific visit are missing in which case the data is excluded from the listing.
 
• Data below the limit of quantification (BLQ) is not missing data and must be displayed as such and included in all listings and summaries.
 

Outliers	
 
• Any subjects excluded from the summaries and/or statistical analyses because their values are considered outliers will be documented along with the reason for exclusion in the CSR.
 

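### Does the SAP's own rule for very low eosinophil counts, which differs from the protocol's, call for a correction?

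*SAP*

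**What the plan says.** The two documents treat low blood eosinophil values differently.

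- Protocol Section 9.4.3, on the ratio to baseline: "Values below the lower limit of quantification will be imputed as half the lower limit of quantification".
- SAP Section 9, on values about to be log-transformed: "Non-detectable values of 0 GI/L, will be replaced by half of the lowest observed detectable (non-zero) value in the study data set".
- SAP Section 2.1, after naming one added analysis population: "There are no other changes to the protocol defined statistical analysis plan".

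Two other SAP rules come close but do not settle the matter. In Section 14.3.2, "Assign zero to non-quantifiable (NQ) values" sits under pharmacokinetic concentration data. In Section 14.5.2, "Data below the limit of quantification (BLQ) is not missing data and must be displayed as such and included in all listings and summaries" keeps such results in the displays but gives no substitute value. Protocol Section 9.3 leaves the full analysis detail to the reporting and analysis plan.

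The endpoint concerned is "Ratio to baseline of blood eosinophils at Weeks 4, 8 and 12". Both documents class it under Other, below the primary and secondary endpoints.

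**The concern.** The rules differ in two respects. The protocol covers every value below the limit of quantification; the SAP covers only values of exactly 0 and is silent on a non-zero value below the limit. The protocol's substitute is fixed by the assay, whereas the SAP's depends on the smallest non-zero count that happens to be observed.

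On a log scale the substitute matters, because a few very small values can pull on the geometric mean, its confidence interval and the log SD. Low values are to be expected, since the drug lowers blood eosinophils. If the rules gave materially different results, the reported ratio to baseline would depend on which document the programmer followed, and a reader relying on SAP Section 2.1 would not know that a choice had been made.

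**Working it through.** No figure in either document depends on this rule, so there is nothing to reproduce. The documents also give no eosinophil quantification limit, reporting step or expected share of low values. The numbers below therefore show what the rules can do under stated assumptions; they are not estimates for this trial.

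**Notation.** L is the limit of quantification, m the lowest non-zero value in the data set, p the share of zeros at a visit, q the share of non-zero values below L, and g the geometric mean of those values.

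**General formula.** The SAP sets zeros to m/2 and keeps non-zero values as reported. The protocol sets all values below L to L/2. On the log scale the two means differ by p·log(m/L) + q·log(2g/L), so

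SAP geometric mean / protocol geometric mean = (m/L)^p × (2g/L)^q.

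**Case A: all results below L are returned as 0** (q = 0, so m is at least L). The factor is (m/L)^p:

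| m | p = 5% | p = 10% | p = 20% |
|---|---|---|---|
| L | 1.000 | 1.000 | 1.000 |
| 1.5 L | 1.020 | 1.041 | 1.084 |
| 2 L | 1.035 | 1.072 | 1.149 |

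The 2 L row is probably near the upper end, on this reasoning. The protocol expects that "158 enrolled subjects should provide at least 150 subjects with complete study data", and the mock table of absolute counts (TAB_PD1) has 5 visits, giving at most 158 × 5 = 790 values. Zeros at 5% to 20% would be about 40 to 158 of them, yet none of the rest could lie between L and 2 L. This is a plausibility argument and not a bound: at m = 5 L the factor would be 1.084 for p = 5% and 1.380 for p = 20%.

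**Ratio to baseline in Case A.** The substitute can enter numerator and denominator, so the factor is (m/L)^(p_post − p_base). At m = 2 L:

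- equal shares of zeros: 1.000
- 20% post, 15% baseline: 2^0.05 = 1.035
- 20% post, 0% baseline: 2^0.20 = 1.149
- 15% post, 20% baseline: 2^(−0.05) = 0.966
- 0% post, 20% baseline: 2^(−0.20) = 0.871

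The last two cannot be excluded, because subjects already on mepolizumab may enrol and can have low counts at Week 0. The direction is therefore unknown.

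**Case B: some non-zero results below L are reported.** With m = 0.5 L and g = 0.75 L, the factor is 0.5^p × 1.5^q:

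- p = 10%, q = 10%: 0.933 × 1.041 = 0.972
- p = 20%, q = 5%: 0.871 × 1.020 = 0.888
- p = 5%, q = 20%: 0.966 × 1.084 = 1.048

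**Simulation.** Log-normal counts with log SD 0.8 were rounded to 0.01 GI/L. With L = 0.05 GI/L, the SAP-to-protocol ratio of geometric means was 0.948 for a true geometric mean of 0.04 GI/L (56% of values below L) and 1.013 for 0.06 GI/L (36% below L). With L = 0.01 GI/L it was 1.000, because every result below the limit is then a 0 and the lowest non-zero value equals the limit.

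**What the rule can reach.** SAP Section 14.8.4 uses these values in Tables 9.1 to 9.6 and Figures 9.1 to 9.4. The tables also give medians, and for absolute counts the median is the same under either rule while fewer than half the values lie below L. SAP Section 9 lists individual counts and ratios. Protocol Section 9.3.2 makes all analyses descriptive.

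**The case for a change.** The strongest case for a change runs as follows. If an added population for screen failures was worth declaring, so was a different imputation rule for a named endpoint. Leaving detail to the reporting and analysis plan allows elaboration, but the protocol stated this rule outright. Cancellation in the ratio is least likely in subjects not on mepolizumab at entry. Protocol Section 5.3 requires of them at least 150 cells/µL at Visit 1 or at least 300 in the previous 12 months, so few zeros are expected at baseline and more after treatment. Protocol Section 4.4 says their pharmacodynamic response is of interest, and the SAP tabulates it separately. The remedy would cost one line.

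Much of this stands: the rules differ as worded, SAP Section 2.1 omits the difference, and the effect need not cancel in that subgroup. It does not follow that the SAP rule is worse. By calling 0 GI/L non-detectable, SAP Section 9 treats 0 as the way a low result appears in the data. If so, the lowest non-zero value stands in for the limit, and half of it has the same form as the protocol's rule. Neither document confirms that reading. The substitute depends on the data, but its formula is set beforehand, leaves the analyst no discretion, and yields one constant for every visit and subgroup.

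**Conclusion.** No change to the plan follows. The discrepancy is a documentation slip: the SAP words a low-value rule differently from the protocol and does not say so. Followed as written, SAP Section 9 still gives a sound descriptive summary. Declaring the rule in SAP Section 2.1 would make the record tidier but change no result. Moving to half the limit is not shown to be an improvement when neither document states a limit.

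The effect cannot be sized from the documents and may be nil. With zeros at up to 20% of values, the lowest non-zero value at most twice the limit and no non-zero results below it, the absolute geometric mean is multiplied by 1.00 to 1.15 and the ratio to baseline by 0.87 to 1.15. The three Case B examples run from 0.89 to 1.05. Every input to these ranges is assumed, and a more extreme lowest value would widen them. The primary and secondary endpoints and the sample size do not depend on the rule, and no hypothesis is tested.

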## 10. EXACERBATIONS

Analyses of exacerbations will be based on the “All Subjects (Safety)” population. The number and percentage of subjects with at least one on-treatment exacerbation will be summarised. On-treatment exacerbations are defined in Section [14.2.1.2](#). All exacerbation data will be listed.

## 11. SAFETY ANALYSES

Analysis of safety data will be based on the ‘All Subjects (Safety)’ population.

### 11.1. Adverse Event Analyses

Adverse event analyses including the analysis of AEs, SAEs and other significant AEs will be based on GSK Core Data Standards. The details of the planned displays are provided in [Appendix 8](#): List of Data Displays.

#### 11.1.1. Adverse Events of Special Interest

Adverse events of special interest (AESIs) are AEs associated with the identified and potential risks of mepolizumab. AESIs reported by the investigator as anaphylaxis reactions, systemic reactions (further categorised by the investigator as either allergic [type I hypersensitivity] or other systemic reactions) and local injection site reactions are collected via targeted eCRF within the study.

AESIs of opportunistic infections, malignancies, serious cardiac, vascular and thromboembolic (CVT) events and serious ischemic events will be identified from a list of relevant preferred terms maintained within a project level reference dataset created based on the MedDRA dictionary available at the time of DBF for this study. Further details of how relevant preferred terms are identified are given in the Program Safety Analysis Plan (PSAP).

Separate summary tables showing the number and percent of subjects with each type of AESI, broken down by preferred term will be created.

For each type of AESI a profile summary table will be produced containing information including, but not limited to, the number of occurrences of the event, event characteristics, time to onset, intensity, outcome and action taken.

Separate listings of AESIs identified by the investigator as anaphylaxis, allergic (type I hypersensitivity), other systemic reactions and local injection site reactions will be produced, as well as listings of opportunistic infections, malignancies, serious CVT events and serious ischemic events.

### 11.2. Clinical Laboratory Analyses

Laboratory evaluations including the analyses of Chemistry laboratory tests, Haematology laboratory tests and liver function tests will be based on GSK Core Data Standards. The details of the planned displays are provided in [Appendix 8](#): List of Data Displays.

A scatter plot of maximum ALT vs baseline ALT, and maximum ALT vs total bilirubin will be produced. In addition, if any liver stopping or liver monitoring events occur during the study, summaries of liver monitoring/stopping event reporting and hepatobiliary laboratory abnormalities will be produced.

### **11.3. Other Safety Analyses**

The analyses of non-laboratory safety test results including ECGs and vital signs will be based on GSK Core Data Standards, unless otherwise specified. The details of the planned displays are presented in [Appendix 8: List of Data Displays](#).

#### **11.3.1. Injection Pain Assessment**

Injection pain assessed immediately after the injection and at 1 and 24 hours post-injection, will be summarised by visit and time point. Summary statistics of the Visual Analogue Scale (VAS) score for injection pain will be presented. Categorical summaries of pain description (sharp/stinging, dull/aching, burning, other), pain relative to expectation (greater than expected, less than expected, as expected) and acceptability of pain will also be summarised. All injection pain data will be listed.

## **12. IMMUNOGENICITY ANALYSES**

### **12.1. Overview of Immunogenicity Analyses**

For the immunogenicity assessment, two types of anti-drug antibody (ADA) assays will be performed, a binding antibody assay and a neutralising antibody assay.

For the binding assay, there will be a three tiered analysis: screening, confirmation and titration. The screening assay produces a result of positive or negative relative to a screening cut point. Positive samples continue with the confirmation assay, which also produces a result of positive or negative relative to a confirmation cut point. For positive confirmation samples, a titre value will also be obtained to quantify the degree of binding in a titration assay and the sample will be tested with the neutralising assay, which also reports results as positive or negative.

The binding ADA results at Week 0 and Week 12/Early withdrawal will be summarised by visit. Summary statistics for the titre result at Week 12/Early Withdrawal will also be presented. Summaries will also be produced by visit and baseline mepolizumab use.

A summary of adverse events by Week 12/Early Withdrawal binding ADA result will be produced.

A summary of liquid treatment emergent positive confirmatory binding ADA assays in the subset of subjects who did not have a positive confirmatory binding ADA assay prior to the first dose of liquid study treatment at Week 0 will also be presented.

Neutralising antibody assay results will be summarised by visit, and by visit and baseline mepolizumab use.

Immunogenicity data will be listed for subjects with at least one positive screening binding assay.

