Potential risk of immunogenicity	
 
Biopharmaceutical products may elicit anti- drug antibody (ADA) and neutralising antibody (NAb), which have the potential to modulate pharmacokinetic (PK), pharmacodynamic (PD) or produce adverse reactions.
 
Mepolizumab has low immunogenic potential. Both incidence and titer data from completed studies demonstrate a low risk for loss of efficacy associated with AEs and/or altered PK/PD. Immunogenicity data reported to date across the mepolizumab development program are summarized in the IB; See Section 5.4 'Clinical Immunogenicity' and a summary of immunogenicity findings in Section 6 'Other Potentially Clinically Relevant Information for the Investigator' [GSK Document Number CM2003/00010/12].
 
	Blood samples will be collected for detection of both ADA and NAb.
	Study Procedures	
Injuries due to accidental needle sticks	The autoinjector has been designed and verified to comply with ISO23908 'Sharps injury protection – Requirements and test methods – Sharps protection features for single-use hypodermic needles, introducers for catheters and needles used for blood	The subject will be educated by the staff prior to self-administration and their first scheduled dose will be supervised in the clinic by the staff. Additionally, the IFU will instruct the subject on the safe use of

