# 7.10. Pharmacokinetics

Blood samples for analysis of mepolizumab plasma concentration will be obtained as per the Time and Events table (Section 7.1). Samples obtained at Visits 2, 3, 4 and 5 should be drawn prior to dosing. The date and exact time of collection for each sample will be documented in the eCRF.

Details for collection and processing of samples may be found in the SRM.

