8.8	PK	-	Scatter Plot of Individual Plasma Mepolizumab Concentration-Time Data by Week 12 Binding Antibody Result	Use grey open circles for data points for subjects with negative binding antibody. Use larger filled blue circles for data points for subjects with positive binding antibody, and annotate data points with subject number.	SAC
Pharmacokinetic – Tables					
8.1	PK	PK01	Summary of Plasma Mepolizumab Concentration-Time Data		SAC
8.2	PK	PK01	Summary of Plasma Mepolizumab Concentration-Time Data by Baseline Mepolizumab Use		SAC
8.3	PK	PK01	Summary of Plasma Mepolizumab Concentration-Time Data by Baseline Mepolizumab Use and Injection Site – Subjects Using the Same Injection Site Throughout the Study	Include only the subset of subjects using the same injection site for all doses of study treatment.	SAC

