**14.8.4. Pharmacodynamic Analyses**

No.	Population	IDSL / TST ID / Example Shell	Title	Programming Notes	Deliverable [Priority]
Pharmacodynamic – Figures					
9.1	PD	FIG_PD1	Geometric Mean (95% CI) Absolute Blood Eosinophils by Visit and Baseline Mepolizumab Use	Include (N=XX) in legend.	SAC
9.2	PD	FIG_PD1	Geometric Mean (95% CI) Absolute Blood Eosinophils by Visit, Baseline Mepolizumab Use and Injection Site – Subjects Using the Same Injection Site Throughout the Study	Baseline mepolizumab use as by-line. Separate lines on graph corresponding to injection sites. Include only the subset of subjects using the same injection site for all doses of study treatment. Include (N=XX) in legend.	SAC
9.3	PD	FIG_PD1	Geometric Mean (95% CI) Ratio to Baseline Blood Eosinophils by Visit and Baseline Mepolizumab Use	Include (N=XX) in legend.	SAC
9.4	PD	FIG_PD1	Geometric Mean (95% CI) Ratio to Baseline Blood Eosinophils by Visit, Baseline Mepolizumab Use and Injection Site – Subjects Using the Same Injection Site Throughout the Study	Baseline mepolizumab use as by-line. Separate lines on graph corresponding to injection sites. Include only the subset of subjects using the same injection site for all doses of study treatment. Include (N=XX) in legend.	SAC

No.	Population	IDSL / TST ID / Example Shell	Title	Programming Notes	Deliverable [Priority]
9.5	PD	-	Scatter Plot of Individual Blood Eosinophil-Time Data by Week 12 Binding Antibody Result	Use grey open circles for data points for subjects with negative binding antibody. Use larger filled blue circles for data points for subjects with positive binding antibody, and annotate data points with subject number.	SAC
Pharmacodynamic – Tables					
9.1	PD	TAB_PD1	Summary of Blood Eosinophils (GI/L) by Visit		SAC
9.2	PD	TAB_PD2	Summary of Ratio to Baseline Blood Eosinophils by Visit		SAC
9.3	PD	TAB_PD3	Summary of Blood Eosinophils by Visit and Baseline Mepolizumab Use		SAC
9.4	PD	TAB_PD4	Summary of Ratio to Baseline Blood Eosinophils by Visit and Baseline Mepolizumab Use		SAC
9.5	PD	TAB_PD3	Summary of Blood Eosinophils by Visit, Baseline Mepolizumab Use and Injection Site– Subjects Using the Same Injection Site Throughout the Study	Add baseline mepolizumab use to by line, and include injection site in first column. Include only the subset of subjects using the same injection site for all doses of study treatment.	SAC

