**CONFIDENTIAL**

204959

No.	Population	IDSL / TST ID / Example Shell	Title	Programming Notes	Deliverable [Priority]
Safety : Figures					
11.5	All Subjects	AE5A	Summary of All On-Treatment Adverse Events by Maximum Intensity by System Organ Class and Preferred Term		SAC
11.6	All Subjects	AE1	Summary of All Drug-Related Adverse Events by System Organ Class and Preferred Term		SAC
11.7	All Subjects	AE5A	Summary of All Drug-Related Adverse Events by Maximum Intensity by System Organ Class and Preferred Term		SAC
11.8	All Subjects	AE1	Summary of On-Treatment Adverse Events by Week 12 Binding Antibody Result	Add in row with n in each binding antibody result category. See Section 12.	SAC
11.9	All Subjects	AE3	Summary of All Adverse Events Leading to Permanent Discontinuation from Study Treatment and/or Withdrawal from the Study by Overall Frequency		SAC
11.10	All Subjects	AE1	Summary of Adverse Events Reported on the Day of Dosing by System Organ Class and Preferred Term		SAC
11.11	All Subjects	AE7	Listing of Subject Numbers for Individual On-Treatment Adverse Events		SAC
11.12	All Subjects	AE2	Listing of Relationship of Adverse Event, System Organ Classes, Preferred Terms and Verbatim Text		SAC
Serious Adverse Events					
11.13	All Subjects	AE3	Summary of Fatal Serious Adverse Events by Overall Frequency		SAC
11.14	All Subjects	AE3	Summary of Drug-Related Fatal Serious Adverse Events by Overall Frequency		SAC

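### Three displays relate outcomes to antibody status by the last sample only, so a subject positive at Week 0 and negative at Week 12 is shown as antibody-negative

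*SAP*

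**What the plan says.** **Sampling.** The Time and Events tables (Protocol 7.1, SAP 14.1.1) schedule immunogenicity at Visit 2, before dosing, and at Visit 5. SAP 12.1 adds: "The binding ADA results at Week 0 and Week 12/Early withdrawal will be summarised by visit".

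**Displays that relate antibody to an outcome.** There are three:
- SAP 14.8.6, Table 11.8: "Summary of On-Treatment Adverse Events by Week 12 Binding Antibody Result". Its programming note points to Section 12, where the rule reads "A summary of adverse events by Week 12/Early Withdrawal binding ADA result will be produced".
- SAP 14.8.3, Figure 8.8: "Scatter Plot of Individual Plasma Mepolizumab Concentration-Time Data by Week 12 Binding Antibody Result".
- SAP 14.8.4, Figure 9.5: "Scatter Plot of Individual Blood Eosinophil-Time Data by Week 12 Binding Antibody Result".

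Both figures carry the same programming note: "Use grey open circles for data points for subjects with negative binding antibody". Positive subjects get larger filled blue circles annotated with the subject number.

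**Displays that use the Week 0 result.** Tables 12.1 and 12.2 give antibody results by visit. Table 12.3 is restricted to subjects without a positive at Week 0. Listing 40 covers every subject with a positive screening assay. None of these shows adverse events, concentrations or eosinophils.

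**Who may be positive at Week 0.** Inclusion criterion 3b (Protocol 5.1) admits subjects already on mepolizumab for at least 12 weeks. The mock table TAB_POP5 (SAP 14.9) lists three earlier mepolizumab trials from which subjects may come.

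**The concern.** Protocol 4.6.1 gives the reason for testing: biopharmaceuticals may elicit antibodies, "which have the potential to modulate pharmacokinetic (PK), pharmacodynamic (PD) or produce adverse reactions". The three displays are the only place in the SAP where that possibility is examined against outcomes. For an event soon after the first dose, or a concentration measured early in the study, the sample nearest in time is the one taken at Week 0. The displays ignore it and use a sample taken about 12 weeks later.

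The analyses are descriptive and no model follows, so the column and symbol labels are what the reader takes away. A reader will naturally understand the negative group as subjects in whom no antibody was found. Under the SAP rule that is not so for one pattern of results, and the SAP itself foresees Week 0 positives, since Table 12.3 sets them apart.

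**Working it through.** The documents give no figure on this point to reproduce. The check is of a classification rule, followed by a bound on its effect.

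**1. The four possible patterns**

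| Week 0 | Week 12 | Group under the SAP | Any positive result? |
|---|---|---|---|
| + | + | positive | yes |
| + | − | **negative** | yes |
| − | + | positive | yes |
| − | − | negative | no |

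Only the second row is placed in a group that contradicts the subject's own data.

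**2. Timing.** Protocol 7.10 says of the PK samples: "Samples obtained at Visits 2, 3, 4 and 5 should be drawn prior to dosing". The Time and Events tables put the Visit 2 haematology and immunogenicity samples before dosing too. Neither figure excludes Week 0. A subject in the second row therefore has Week 0 concentration and eosinophil values drawn as antibody-negative although the antibody sample of that same visit was positive.

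**3. Effect on the positive column of Table 11.8.** Let n be the number of ever-positive subjects (n at least 2), one of whom is +/−. Let x be the number of the other n − 1 with an event.
- If the +/− subject had an event, the rate goes from (x + 1)/n to x/(n − 1), a fall of (n − 1 − x)/[n(n − 1)]. The largest value is 1/n, reached only when x = 0.
- If the +/− subject had no event, the rate goes from x/n to x/(n − 1), a rise of x/[n(n − 1)], again at most 1/n.

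To put numbers in, assume that 2% to 6% of the 158 planned subjects are ever positive: 158 × 0.02 = 3.2 and 158 × 0.06 = 9.5, so n is about 3 to 9.
- Ceiling: 1/3 = 33 points at n = 3, and 1/9 = 11 points at n = 9.
- n = 3, x = 1: 2/3 becomes 1/2, a fall of 17 points.
- n = 9, x = 4: 5/9 becomes 4/8, a fall of 6 points.
- All the others had an event (x = n − 1): no change.
- n = 6, x = 3, +/− subject without an event: 3/6 becomes 3/5, a rise of 10 points.

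**4. Effect on the negative column.** With n = 9 there are 158 − 9 = 149 never-positive subjects. Adding one changes that rate by at most 1/150, or 0.7 points.

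**5. How many subjects.** The expected number is N × P(positive at Week 0) × P(negative at Week 12 given positive at Week 0). With N = 158 and both probabilities assumed:
- 1% and 25%: 158 × 0.01 × 0.25 = 0.4
- 3% and 50%: 158 × 0.03 × 0.50 = 2.4, with a chance of at least one of 1 − (1 − 0.015)^158 = 0.91
- 10% and 75%: 158 × 0.10 × 0.75 = 11.9

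The range is wide because neither probability is in the documents.

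**The case against.** **The information is not lost.** A confirmed Week 0 positive must first be screening-positive, so every such subject is in Listing 40. Adverse events, concentrations and eosinophils are listed by subject (Listings 22, 20 and 41). For a handful of subjects, matching by hand is feasible. This stands, and it is the main reason why the point is minor. It does not make the group labels right.

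**An ever-positive group has its own drawback.** The safety objective concerns the liquid product in the autoinjector, and Week 0 antibody predates it. Pooling would mix carried-over antibody with antibody that arose during the study. This also stands. It argues for a separate category, not for leaving these subjects among the negatives.

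**Stronger readings that the documents do not support:**
- *The rule biases every comparison towards no effect.* The positive rate can fall, rise or stay the same, depending on the moved subject and on the others. No formal comparison is planned.
- *A shift of 11 to 33 points is typical.* Those values are the ceiling 1/n under an assumed n. They do not apply to Figures 8.8 and 9.5, which plot individual values and contain no group rate.
- *The events nearest the first dose are the ones misplaced.* Classification is by subject, so all of that subject's on-treatment events move, up to 28 days after the last dose (SAP 14.2.1.1).
- *Early withdrawals drop out of the figures.* Visit 5 is a single column for End of Study and Early Withdrawal, and Section 12.1 and Tables 12.1 to 12.3 treat the two as one time point. SAP 14.3.2 does re-assign early-withdrawal data to the next scheduled visit, so the titles should be explicit, but this is a matter of wording.

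**Conclusion.** The point holds as a minor misclassification in three supportive displays. That a +/− subject is shown as antibody-negative follows from the SAP text and needs no assumption. How often it will happen is unknown: the documents give no antibody or reversion rate, and Protocol 4.6.1 describes low immunogenic potential. For Table 11.8 the effect of one such subject is bounded by 1/n in the positive column and is negligible in the negative column. The bound looks large only because the positive group is likely to be small. A reader might infer that the plan hides an antibody effect. The documents do not support that: the direction is open and the individual results are listed. The primary endpoint, injection success at Week 8, is not touched.

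**What to change.** In SAP 12.1, Table 11.8 and Figures 8.8 and 9.5, define antibody status from the confirmed binding result at both Week 0 and Week 12/Early Withdrawal. Show subjects positive at Week 0 and negative at Week 12 as their own column in the table and their own labelled symbol in the figures. An acceptable alternative is an ever-positive group with Week 0 positives marked separately. Either way they should not be shown within the negatives.

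Change the three display titles to Week 12/Early Withdrawal, to match Section 12.1.

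The cost is one derived flag, three revised displays and a sentence in the SAP. Table 12.3 already requires Week 0 status, so no new samples, data collection or protocol change is needed.
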